### 8.3. RECORDING

AE data should be obtained through observation of the patient, from any information volunteered by the patient, or through patient questioning.

All AEs (serious and non-serious) which occur from signature of the informed consent through patient participation in the study (last planned visit or early withdrawal date) will be reported and recorded in the eCRF. It is important that the AE dedicated pages of the eCRF includes the duration of the AE (onset/resolution dates), the relationship to the drug, the severity, the outcome, the action(s) taken and relevant concomitant treatments dispensed.

All AEs should be followed-up to determine outcome of the reaction. The Investigator should follow up the event until resolution or stabilization of the condition. It is the Investigator’s responsibility to assure that the subjects experiencing an AE receive definite treatment for any AE, if required.

Medical conditions/diseases present before starting study treatment shall be documented in the medical history section of the eCRF; these conditions are considered AEs only if they increase either in frequency or severity once informed consent has been signed.

#### 8.3.1. Relationship of AEs to the Investigational Product

The Investigator will assess the causal relationship between the AE and the IMP (either ladarixin or placebo), according to the criteria in **Table** below:

### Relationship of the Adverse Event to the IMP

None (Intercurrent Event)	An event that is not and cannot be related to the Investigational Product, e.g. a surgical intervention for nevus removal performed during the study, but planned before patient enrolment into the study
Unlikely (remote)	Relationship is not likely e.g. a clinical event including laboratory test abnormality with temporal relationship to drug administration which makes a causal relationship improbable and in which other drugs, chemicals or underlying disease provide more plausible explanations
Possible	Relationship may exist, but could have been produced by the patient's condition or treatment or other cause
Probable	Relationship is likely, the AE abates upon discontinuation of Investigational Product and cannot be due to the patient's condition
Highly Probable	Strong relationship, the event abates upon discontinuation of Investigational Product and, if applicable, re-appears upon repeat exposure

Any AE reported in the study having a possible, probable or highly probable relationship to study drug will be considered as an ADR.

#### 8.3.2. Severity of AEs

The Investigator will grade the severity of any AE using the definitions in the **Table** below. For each episode, the highest severity grade attained should be reported.

#### Severity of the Adverse Event

Mild	Grade 1 - Does not interfere with patient's usual function (awareness of symptoms or signs, but easily tolerated [acceptable]).
Moderate	Grade 2 - Interferes to some extent with patient's usual function (enough discomfort to interfere with usual activity [disturbing]).
Severe	Grade 3 - Interferes significantly with patient's usual function (incapacity to work or to do usual activities [unacceptable])

### 8.4. SERIOUS ADVERSE EVENT REPORTING

#### 8.4.1. Reporting Procedure for Investigators to Dompé

The Investigator must report all SAEs occurring during patient participation in the study, regardless of presumed causal relationship, to the CRO Pharmacovigilance contact and to Dompé Drug Safety Department, by e-mail (preferred) or fax **within 24 hours** of learning of the event. Contact details for SAE reporting by the Investigator are provided in the section "Contact Information".

The Investigator should also report information on SAEs that continue after patient has completed his/her participation in the study (whether study completion or withdrawal), unless patient has withdrawn his/her consent.

In line with CT3 Detailed Guidance and ICH E2A provisions, although the Investigator does not usually need to actively monitor patients for AEs once the trial has ended, if the Investigator becomes aware of a SAE occurring to a patient after that patient has ended his/her participation in the study (whether study completion or withdrawal), the SAE should be reported by the Investigator to the CRO Pharmacovigilance or directly to the Dompé Drug Safety department, should the whole study have been ended. Such "post-study cases" should be regarded for expedited reporting purposes as though they were study reports. Therefore, a causality assessment and determination of expectedness are needed for a decision on whether or not expedited reporting is required.

Information on SAEs will be recorded on a specific SAE form. Both electronic and blank paper copies will be included in the Investigator's Site File. Follow-up reports (as many as required) should be completed and e-mailed/faxed following the same procedure above.

Whenever more than one SAE is observed, the Investigator should identify which is the primary adverse event, i.e. the most relevant one. If other events are listed in the same report, the Investigator, along with their relatedness to the Investigational Product, should identify which adverse events are serious and which are non-serious. In any case, the Investigator is requested to record his/her opinion about the relatedness of the observed event(s) with the investigational medication.

#### **8.4.2. Conditions that should not be reported as serious adverse events**

The conditions listed below, that may require hospitalization of a patient, are not considered to be SAE and shall not be reported as such, but only need to be recorded in the CRF:

- Hospitalizations planned before entry into the clinical study which is part of the normal treatment or monitoring of the studied indication and not associated with any deterioration in condition.
- Hospitalization for routine treatment or monitoring of the studied indication, not associated with any deterioration in condition.
- Hospitalization for treatments, which was elective or pre-planned, for a pre-existing condition that is unrelated to the indication under study and did not worsen.
- Treatment on an emergency, outpatient basis for an event not fulfilling any of the definitions of SAEs given above and not resulting in hospital admission.

In addition, the following situation shall not be considered SAE:

- Abnormal lab values or test results that do not induce clinical signs and/or symptoms and require intervention/therapy, i.e. are clinically significant.

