### Discontinuation criteria

Administration of the investigational medicinal product will be discontinued in case the QTcF becomes either >500 msec. or increases by >60 msec. from baseline measurement on two consecutive measurements 1 hour apart, or if the patient develops any significant cardiovascular disease/abnormality. Similarly, administration of the investigational medicinal product will be discontinued in the case the patient develops renal (eGFR <60mL/min/1.73 m^2) or hepatic (ALT/AST >3 x ULN and total bilirubin >3mg/dL) dysfunction as well as hypoalbuminemia (serum albumin <3 g/dL). Lastly, administration of the investigational product will be immediately discontinued if the patient becomes pregnant, develops any significant systemic infection that must be assessed on a case-by-case basis by the investigator regarding whether they are serious enough to warrant discontinuation, ketoacidosis or hypoglycemic coma. Occurrence of any condition that qualify the patient to treatment discontinuation will be specifically monitored through ECG readings and laboratory tests obtained at visits scheduled at the end of the 3rd (Week 11), 6th (Week 23), 9th (Week 35) treatment cycles. In addition, the investigational medicinal product will be immediately discontinued in the event of any other possibly drug related occurrences that the Investigator believes might compromise patient's safety.

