## 8. ADVERSE EVENTS

### 8.1. DEFINITIONS

#### 8.1.1. Adverse Event

An adverse event (AE) is defined as any untoward medical occurrence in a patient or clinical investigation subject administered a medicinal product and which does not necessarily have a causal relationship with this treatment. An AE can therefore be any unfavorable and unintended sign (including an abnormal laboratory finding), symptom, or disease temporally associated with the use of a medicinal product, whether or not related to the medicinal product.

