#### 8.1.3. Serious Adverse Event/Reaction

A Serious Adverse Event (SAE)/Reaction is defined as any untoward medical occurrence that at any dose:

- results in death. Death shall always be reported as SAE and cause of death shall always be specified when known.
- is life-threatening (i.e. the patient was at risk of death at the time of the event. It does not refer to an event which hypothetically might have caused death if it were more severe),
- requires inpatient hospitalization or prolongation of existing hospitalization,

*NOTE: In general, hospitalization means that the individual remained at the hospital or emergency ward for observation and/or treatment (usually involving an overnight stay) that would not have been appropriate in the physician's office or an out-patient setting. Complications that occur during hospitalization are AEs. If a complication prolongs hospitalization or fulfills any other serious criteria, the event is serious. When in doubt as to whether “hospitalization” occurred, the event should be considered serious.*

- results in persistent or significant disability/incapacity,

*NOTE: This definition is not intended to include experiences of relatively minor medical significance such as uncomplicated headache, nausea, vomiting, diarrhea, influenza, or accidental trauma (e.g., sprained ankle) which may interfere or prevent everyday life functions, but do not constitute a substantial disruption.* is a congenital anomaly/birth defect,

- is an important medical event that based upon appropriate medical judgment, may jeopardize the patient and may require medical or surgical intervention to prevent one of the outcomes listed above.

*NOTE: An important medical condition is an event that may not result in death, be life-threatening, or require hospitalization but may be considered a SAE when, based upon appropriate medical judgment, it may jeopardize the patient and may require medical or surgical intervention to prevent one of the outcomes listed above. Examples of such medical events include allergic bronchospasm requiring intensive treatment in an emergency room or at home, blood dyscrasias or convulsions that do not result in patient hospitalization, or the development of drug dependency or drug abuse.*

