### 8.2. MONITORING FOR ADVERSE EVENTS

At each visit following study informed consent form signature, after the subject has had the opportunity to spontaneously mention any problem, the Investigator or appropriate designee should inquire about AEs by asking the standard questions:

- “Have you had any health problems since your last study visit?”
- “Have there been any changes in the medicines you take since your last study visit?”

AEs should be reported for any clinically relevant change in concomitant condition(s) that is the result of an untoward (unfavorable and unintended) change in a subject’s medical health. Changes in any protocol-specific systemic parameter evaluated during the study are to be reviewed by the Investigator. Any untoward (unfavorable and unintended) change in a protocol-specific parameter or questionnaire response that is clinically relevant is to be reported as an AE. These clinically relevant changes will be reported regardless of causality.

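### Protocol 8.4.2 appears to have lost a negation: as worded it bars some asymptomatic laboratory or test results that meet the 8.1.3 seriousness criteria from being SAEs

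*Protocol*

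**What the plan says.** Protocol 8.4.2 first lists hospital and emergency contacts that do not count as SAEs. It then adds a separate item, introduced by "In addition, the following situation shall not be considered SAE". The item reads: "Abnormal lab values or test results that do not induce clinical signs and/or symptoms and require intervention/therapy, i.e. are clinically significant".

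Protocol 8.1.3 defines an SAE. Two of its criteria can be met without any symptom. One is an event that "requires inpatient hospitalization or prolongation of existing hospitalization". The other is an important medical event which, on medical judgment, "may jeopardize the patient and may require medical or surgical intervention to prevent one of the outcomes listed above".

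Protocol 8.1.1 makes clear that a laboratory result can be an event in its own right: "An AE can therefore be any unfavorable and unintended sign (including an abnormal laboratory finding), symptom, or disease temporally associated". Protocol 8.2 adds: "Any untoward (unfavorable and unintended) change in a protocol-specific parameter or questionnaire response that is clinically relevant is to be reported as an AE".

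SAE status carries a specific duty in Protocol 8.4.1: "The Investigator must report all SAEs occurring during patient participation in the study, regardless of presumed causal relationship". The report is due within 24 hours of the investigator learning of the event.

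**The concern.** An exclusion of this kind normally keeps trivial out-of-range values out of the SAE system. This one, as printed, points the other way: it names results that need treatment and calls them clinically significant, then says they are not SAEs. An investigator who follows 8.4.2 and one who follows 8.1.3 could classify the same event differently.

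Seriousness decides what happens next. It triggers the 24-hour report (Protocol 8.4.1), the sponsor's assessment of whether the event is a suspected unexpected serious reaction (8.4.4 and 8.4.5), and entry into the serious TEAE and serious ADR outputs (SAP 8.1). An event left non-serious because of this item would bypass all of these. The item covers test results as well as laboratory values, so on its wording it can also reach ECG findings.

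**Working it through.** No arithmetic applies; the check is a comparison of texts.

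**Step 1: what the item excludes.** Let S mean that the result causes signs or symptoms, and T that it requires intervention or therapy. The sentence has one *not*, and its scope is unclear.

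| Reading | Excluded from SAE status | Asymptomatic result needing therapy (not S, T) |
|---|---|---|
| 1. *not* governs only the first verb | not S and T | excluded |
| 2. *not* governs both verbs jointly | not (S and T) | excluded |
| 3. probable intent | not S and not T | not excluded |

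Reading 3 is the harmless one. To state it, the text would need *or* (or *neither/nor*) in place of *and*, and a *not* before the closing words on clinical significance. Neither is printed. Readings 1 and 2 both exclude the asymptomatic result that needs therapy. Reading 1 also gives an odd result: it leaves trivial results (not S, not T) outside the exclusion, which supports the view that a negation was lost.

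**Step 2: comparison with the SAE definition.** For an asymptomatic result that needs therapy:

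- It meets no criterion in 8.1.3: both sections say it is not an SAE, so there is no conflict.
- It leads to inpatient admission or a longer stay: 8.1.3 says SAE; 8.4.2 says not.
- On medical judgment it may endanger the patient and may need intervention to avert one of the serious outcomes: 8.1.3 says SAE; 8.4.2 says not.

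The conflict is therefore confined to the results that also meet a seriousness criterion. Needing treatment is not enough.

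**Step 3: does other text settle it?** The item just before it in 8.4.2, on emergency outpatient treatment, applies only to events that meet none of the SAE definitions. The laboratory item has no such limit, so a site may take it as overriding 8.1.3. Nothing else in the Protocol or SAP corrects it or says which section prevails.

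**Step 4: what depends on the classification.**

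| Depends on SAE status | Does not depend on it |
|---|---|
| 24-hour report (Protocol 8.4.1) | AE reporting of clinically relevant changes (Protocol 8.2) |
| SUSAR assessment (Protocol 8.4.4, 8.4.5) | AE recording and follow-up (Protocol 8.3) |
| Serious TEAE and serious ADR outputs, SAE listing (SAP 8.1) | TEAE and IMP-discontinuation tables (SAP 8.1); laboratory and ECG summaries (SAP 8.2, 8.4) |

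**The case against.** The strongest reply is that the intent is obvious: the closing words make sense only if the item was meant to exclude results that are *not* clinically significant, and an experienced investigator would read it so. That is probably right about intent, and it makes this a wording error and not a chosen policy. It does not cure the text, because sites apply what is printed and the lead-in is categorical.

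The second reply is that little is lost, because such results are still collected as AEs, followed up, and tabulated. This stands. A reader might infer that hepatic or renal signals would go unreported; the documents do not support that. What is at risk is seriousness and the expedited steps that follow from it, which tables at the end of the trial do not replace.

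Two further inferences are tempting and should not be drawn:

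- *That the events which stop study drug are the ones excluded.* The criteria, for example "hepatic (ALT/AST >3 x ULN and total bilirubin >3mg/dL) dysfunction as well as hypoalbuminemia", are laboratory thresholds. But no text says that crossing one is an SAE, or that stopping study drug is the intervention meant in 8.4.2. Many such events would not be serious under 8.1.3 in any case.
- *That the ladarixin patient in the earlier type 1 diabetes trial who stopped for raised ALT and AST (Protocol 2.4.3) shows the size of the problem.* The text does not say that this patient was asymptomatic, needed therapy or met a seriousness criterion. The events were captured as AEs.

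The third reply is that a correction now comes late. SAP section 1 dates the notice stopping enrolment 28 March 2022. Assume nobody consented after that date and insulin had been started by then. With at most 100 days to first dose, the last first dose falls by 6 July 2022. The upper limit of the Month 18 window is 80 weeks, or 560 days, which gives 17 January 2024. That is before SAP version 3.0 of 7 May 2024. On those assumptions a note to sites would change little, and the useful remedy is a check of the data.

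**Conclusion.** The point holds in this form: the laboratory item in Protocol 8.4.2 contradicts 8.1.3 for asymptomatic laboratory or test results that meet the hospitalization or important-medical-event criterion, and no other text resolves it. It is most likely a drafting slip, but it sits in an operative safety-reporting rule.

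The number of events affected cannot be derived from the documents and may be zero. It depends on how sites read the item and on how many qualifying results occurred, and neither is reported. For scale only, Protocol 2.4.3 gives treatment-emergent SAEs in 3 of 50 ladarixin and 1 of 26 placebo patients in the earlier trial, 4 of 76 overall. With counts that low, one reclassified event would be visible in the serious TEAE table. This says nothing about how likely a misclassification is. No efficacy analysis, alpha, power or sample size figure is affected.

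**What to change.** Reconcile the two sections:

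- Reword the item in 8.4.2 so that it excludes only abnormal laboratory or test results that neither cause clinical signs or symptoms nor require intervention or therapy, that is, results that are not clinically significant.
- State that any laboratory or test result meeting a criterion in 8.1.3 is an SAE regardless of 8.4.2. Tying this to the laboratory item leaves the exclusions for planned and routine hospitalization as they are.

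The cost is two sentences in the protocol and a note to sites. It changes no analysis.

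If conduct is complete, have the seriousness of AEs based on laboratory or ECG findings checked against 8.1.3 before the serious TEAE tables are finalised, with investigators queried where it is in doubt. This is best done blind to treatment; the blind data review meeting in SAP 4.9 is a natural place if it has not yet been held. Any event reclassified as serious should then go through the reporting steps in 8.4, and the clinical study report should say that the check was made and what it changed. The cost is one review of a subset of the AE listing.

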#### **8.4.3. Follow-Up of Serious Adverse Events**

If subject was hospitalized due to a SAE, a copy of the discharge summary is to be forwarded to the Sponsor as soon as it becomes available. In addition, a letter from the Investigator that summarizes the events related to the case, as well as results of any relevant laboratory tests and redacted section of medical records may be provided to the Sponsor, if relevant for the SAE. In case of death, a copy of the autopsy report, if performed, should also be provided.

The Investigator shall inform the Sponsor with an appropriate written communication, whenever he becomes aware of new available information regarding the SAE, once the condition is resolved or stabilized and when no more information about the event is expected. Follow-up SAE information should be processed as initial SAE notification (see Par. 8.4.1).

For pharmacovigilance purposes, all SAEs should be followed-up in order to clarify as completely as possible their nature and/or causality and until all queries have been resolved. All SAEs will be followed up until the events resolve or the events or sequelae stabilize, or it is unlikely that any additional information can be obtained after demonstration of due diligence with follow-up efforts (i.e. subject or Investigator is unable to provide additional information, or the subject is lost to follow up), unless subject has withdrawn his/her consent.

#### **8.4.4. Reporting Procedure to IEC and to Regulatory Authorities in the European Union**

##### *Reporting of Suspected Unexpected Serious Adverse Reaction*

Investigator must report all serious adverse events to the sponsor immediately, within 24 hours.

Dompé Drug Safety Department, with the support of the CRO as appropriate, shall report any SUSAR to the concerned IEC which approved the protocol and the Regulatory Authority (via the Eudravigilance Clinical Trial module) as soon as possible, and in no event later than:

- seven calendar days after becoming aware of the information if the event is fatal or life threatening; to be followed by any relevant information within eight days.
- fifteen calendar days after becoming aware of the information if the event is neither fatal nor life threatening.

Treatment will be unblinded by Dompé Drug Safety prior to regulatory submission of a SUSAR to Regulatory Authorities and IEC in the European Union, and only cases referred to active treatment will be considered expeditable for regulatory reporting, in line with law requirements.

If the results of an investigation show that an AE not initially determined to be reportable is reclassified as reportable, Dompé shall notify such SUSAR in a written safety report as soon as possible, but in no event later than 7/15 calendar days after the determination is made.

Copies of all correspondence relating to reporting of any SAEs to the IEC should be maintained in the Investigator's Files.

#### *Periodical Reporting to EU Regulatory Authorities*

The Sponsor Drug Safety Department will prepare and submit (via the CRO as applicable) to Investigators appropriate periodical safety updates as per applicable EU and local requirements and regulations. Dompé Drug Safety Department shall also be responsible to prepare and submit annual safety reports (Development Safety Update Report – DSUR) to relevant Regulatory Authorities and to IECs.

